A Comparison of Horizontal and Vertical Bitewing Radiographs in Detecting Approximal Caries and Interdental Bone Loss in Posterior Teeth: A Diagnostic Accuracy Randomized Cross-Over Clinical Trial

NCT04341636

February 20, 2020

Principal Investigator:

[name]

Departments of Dental Public Health and Periodontology
King Abdulaziz University, Tufts University, Harvard University

Co-Investigators:

[name], [name]
Faculty of Dentistry, King Abdulaziz University

1. Background and Rationale

Bitewing radiographs are a standard diagnostic tool in dental practice, primarily used to detect approximal caries and evaluate interproximal alveolar bone levels. Traditionally, horizontal bitewings have been widely used for these purposes. However, they have limitations in visualizing vertical bone loss, furcation involvement, and root caries.

Vertical bitewing radiographs, by contrast, provide greater visibility of the apico-coronal dimension and root structures, making them potentially more effective for diagnosing periodontal conditions and deeper carious lesions. This study aims to compare the diagnostic accuracy of vertical versus horizontal bitewing images in detecting caries and bone loss in posterior teeth.

2. Objectives

Primary Objective

- To compare the accuracy of vertical versus horizontal bitewing radiographs in detecting approximal caries and alveolar bone loss.

Secondary Objective

- To evaluate the effectiveness of both imaging modalities in identifying furcation involvement.
- To assess the diagnostic clarity and patient suitability for each radiographic approach.

Material and methods:

3. Study Design

This is a two-arm, randomized crossover clinical trial comparing vertical and horizontal bitewing radiographs. The study was conducted at the Faculty of Dentistry, King Abdulaziz University.

Type of Study: Open-label, randomized crossover clinical trial

Study Setting: Faculty of Dentistry, King Abdulaziz University

Registration: ClinicalTrials.gov (NCT04341636)

Ethical Approval: KAU Ethics Committee (#053-06-17)

4. Participants

Inclusion Criteria:

- Age ≥ 18 years
- Presenting for treatment at KAU dental clinics
- Presence of posterior teeth and canines in each quadrant
- No acute periodontal infection
- Non-smokers
- Full ability to open mouth and tolerate X-ray procedures

Exclusion Criteria:

- Systemic conditions complicating treatment
- Pregnancy or lactation
- Prosthesis obscuring CEJ or caries borders

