- Gag reflex or any contraindication to X-ray
- Refusal to participate

5. Interventions

Each participant received:

- Four horizontal bitewing radiographs (control)
- Four vertical bitewing radiographs (experimental)
- Radiographs were taken using a standardized film holder and a 3-mm orthodontic wire attached to the sensor for magnification calibration.

Observers included two restorative specialists (for caries) and two periodontists (for bone loss), all blinded to group assignments.

6. Measurements

- Caries Assessment:

Evaluated using a 5-point diagnostic confidence scale and a secondary clarity scale.

- Bone Loss & Furcation:

Measured from the CEJ to the alveolar crest using calibrated software. Furcation involvement was assessed using a 5-point scale.

- Intra- and Inter-Observer Agreement:

Evaluated with Kappa statistics and intra-class correlation coefficients.

7. Sample Size Calculation

- **Software:** G*Power 3.1.9

- Effect size: 2.1 mean difference

- SD: 5.2

- Power: 80%

- Alpha: 0.05

- Required Sample: 20 patients

8. Statistical Analysis

Statistical Analysis

Software:

Data will be analyzed using IBM SPSS Statistics version 23.0 (IBM Corp., Armonk, NY, USA) and ROC analysis will be performed using MedCalc or equivalent software for diagnostic

accuracy assessment.

8.1 Analysis Population:

All radiographs captured for the 20 enrolled participants (160 total bitewing images: 80 vertical, 80 horizontal) will be included. Both intention-to-treat and per-protocol analyses will be conducted. All images were anonymized, and evaluators were blinded to image type and patient identity.

8.2 Primary Analysis:

Primary Endpoints:

- Detection of approximal caries (presence and clarity)
- Alveolar bone level measurements (in mm)
- Presence and clarity of furcation involvement

Tests for Diagnostic Accuracy:

- **Receiver Operating Characteristic (ROC) Analysis:**

ROC curves were plotted for each evaluator for both vertical and horizontal bitewings.

The Area Under the Curve (AUC) was computed to assess diagnostic accuracy compared to the “gold standard” (combined clinical and radiographic diagnosis).

- AUC values close to 1.0 indicate higher accuracy.
- Comparisons of AUCs between vertical and horizontal bitewings were conducted using DeLong’s test.
- **Sensitivity and Specificity:** These were calculated for each radiographic method in detecting caries and furcation involvement. 95% confidence intervals were provided.

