8.3 Observer Reliability:

- **Intra-Observer Agreement:** Measured using **Weighted Kappa coefficients** for repeated readings of the same radiographs by the same observer at two time points.

- **Inter-Observer Agreement:** Measured using **Intraclass Correlation Coefficient (ICC)** for bone level measurements and **Weighted Kappa** for caries and furcation rating scores between observers.

Interpretation of Kappa values:

- < 0.20: Poor
- 0.21–0.40: Fair
- 0.41–0.60: Moderate
- 0.61–0.80: Substantial
- 0.81–1.00: Almost perfect

8.4 Comparative Tests Between Vertical and Horizontal Bitewings:

- **Wilcoxon Signed-Rank Test:** Used to compare the mean alveolar bone loss measurements (mesial, distal, and total) between vertical and horizontal bitewings (non-parametric paired comparison).
- **McNemar Test:** Applied to assess paired binary outcomes (e.g., presence vs. absence of caries or furcation involvement) between imaging modalities.
- **Chi-Square Test:** Used to compare proportions of overlapping contacts and furcation detection in both modalities.
- **Descriptive Statistics:**
 - Mean \pm standard deviation (SD) for continuous variables (e.g., bone level)
 - Frequencies and percentages for categorical variables (e.g., tooth type, gender distribution)

8.5 Handling of Missing Data:

- Missing image evaluations (if any) were addressed via sensitivity analysis using pairwise deletion, given the minimal expected rate due to controlled data acquisition and blinded

scoring.

8.6 Effect Size Reporting:

- For Wilcoxon and McNemar tests, effect sizes (r) were reported.
- For ROC analysis, 95% CI of AUCs and comparison P-values were provided.

9. Expected Outcomes

- Vertical bitewings will show higher sensitivity in detecting furcation involvement.
- Vertical bitewings will provide better diagnostic accuracy for approximal caries and alveolar bone loss.
- Vertical bitewings will have superior intra- and inter-observer reliability in detecting pathology.

10. Ethical Considerations

- All participants provided informed written consent.
- Ethical approval was secured from local ethics board.
- All data were anonymized and securely stored.
- Participants had the right to withdraw at any time without consequences.

11. Timeline

Phase	Duration
Ethical Approval	Completed
Participant Recruitment	2 months
Radiograph Collection	2 months
Data Analysis	1 month

Phase	Duration
Manuscript	1 month

12. Dissemination Plan

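### Section 8.5 has no rule for sites that one view cannot show or measure; if these are deleted as missing, the visibility part of the difference drops out of the accuracy comparison

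*Combined protocol and SAP*

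**What the plan says.** - **Handling (8.5).** Missing evaluations of images are "addressed via sensitivity analysis using pairwise deletion", "given the minimal expected rate due to controlled data acquisition and blinded" scoring. No rate is given, and no main rule is named against which this sensitivity analysis would be read.
- **Population (8.1).** "All radiographs captured for the 20 enrolled participants" are to be included, 80 per view. This is a rule about images. It does not say what happens to a site within an image that cannot be read.
- **Rationale (1).** Of horizontal bitewings: "they have limitations in visualizing vertical bone loss, furcation involvement, and root caries". Vertical bitewings are said to "provide greater visibility of the apico-coronal dimension and root structures".
- **Measurement (6).** Bone level is "Measured from the CEJ to the alveolar crest using calibrated software". Caries has a 5-point confidence scale and a clarity scale; furcation has a 5-point scale.
- **Comparisons (8.2, 8.4).** Sensitivity, specificity and AUC by view; McNemar on presence v absence; Wilcoxon signed-rank on bone level; and a chi-square test "Used to compare proportions of overlapping contacts and furcation detection in both modalities".

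**The concern.** Failing to show a lesion or a crest is a diagnostic failure of the view. The trial is run because the two views are thought to differ in what they show, so unreadable sites are unlikely to be random or equally frequent in the two arms. The reason given in 8.5 for expecting few missing values is controlled acquisition and blinded scoring. Neither brings a crest that lies outside the field into view, and neither opens an overlapped contact.

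The gap is clearest for bone level. A CEJ-to-crest distance has no value unless both landmarks are visible, and a signed-rank test needs both members of the pair, so such a site drops out by default. For caries and furcation the plan does not say whether an unreadable surface receives a scale score or is left missing. If it is left missing and deleted, the accuracy comparison, which is the primary objective, no longer includes the part of the difference that comes from visibility. A small overall rate of loss would not settle the matter if the lost sites are mostly the diseased ones.

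**Working it through.** The plan gives no rate of missing or unreadable sites, so there is no figure of its own to reproduce. Every rate and distribution below is an assumption.

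**1. Caries and furcation sensitivity**

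Inputs, for diseased sites: sV and sH are the sensitivities on readable sites; w and u are the unreadable rates for vertical and horizontal. Readability is taken as independent of detectability in the other view.

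- All sites, unreadable counted as not detected: D_all = sV(1 − w) − sH(1 − u).
- Sites readable in both views only: D_del = sV − sH.
- Part lost by deletion: D_all − D_del = sH·u − sV·w, which is 0.80(u − w) when both sensitivities are 0.80.

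With sV = sH = 0.80, D_del is 0 throughout:

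| u (horizontal) | w (vertical) | Horizontal, all sites | Vertical, all sites | D_all |
|---|---|---|---|---|
| 2% | 0% | 78.4% | 80.0% | 1.6 points |
| 5% | 1% | 76.0% | 79.2% | 3.2 points |
| 10% | 2% | 72.0% | 78.4% | 6.4 points |
| 20% | 5% | 64.0% | 76.0% | 12.0 points |

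The zero follows from setting the two sensitivities equal. With sV = 0.80 and sH = 0.70:

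- u = 10%, w = 0: D_all = 0.80 − 0.70 × 0.90 = 17 points, against 10 after deletion. An advantage on readable sites survives; only the visibility part is lost.
- u = 5%, w = 10%: D_all = 0.80 × 0.90 − 0.70 × 0.95 = 0.720 − 0.665 = 5.5 points, against 10 after deletion. When vertical is the less readable view, deletion overstates its advantage.

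McNemar moves in the same way. With 100 diseased sites, u = 10%, w = 0 and sensitivity 0.80, deletion removes 100 × 0.10 × 0.80 = 8 vertical-only detections and no horizontal-only ones.

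**2. Bone level: which sites are lost**

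Assume the CEJ-to-crest distance is log-normal with median 2.5 mm and log SD 0.45, and that one view cannot show the crest beyond a limit c. The share lost is P(X > c) = 1 − Φ(ln(c/2.5)/0.45).

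- P(X ≥ 4) = 1 − Φ(1.044) = 14.8%.
- c = 5 mm: 1 − Φ(1.540) = 6.2% of all sites, and 6.2/14.8 = 42% of sites at or above 4 mm.
- c = 6 mm: 1 − Φ(1.945) = 2.6% of all sites, and 17% of sites at or above 4 mm.

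**3. Bone level: is the mm difference biased?**

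Under the same model with c = 5 mm, the mean over all sites is 2.5 × exp(0.45²/2) = 2.77 mm. The mean over sites below 5 mm is 2.77 × Φ(1.540 − 0.45)/Φ(1.540) = 2.77 × 0.862/0.938 = 2.54 mm.

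- Horizontal reads a constant 0.30 mm low: the paired difference is 0.30 mm with or without deletion.
- Horizontal reads 10% low: 0.28 mm over all sites, 0.25 mm after deletion.
- No true difference, but each view keeps all the sites it can measure: 2.77 − 2.54 = about 0.22 mm appears, away from no difference.

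So part 2 shows loss of deep sites. It does not by itself show a biased mm difference.

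**The case against.** A reader might infer that pairwise deletion removes the very advantage under test and biases the main comparison towards no difference. The documents do not support that, for four reasons.

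- **The wording.** Section 8.5 concerns missing image evaluations. It does not say that a site which was read but not visible is coded missing. Deletion is called a sensitivity analysis and the main rule is unstated, so bias in the main result is not established.
- **Visibility is partly captured elsewhere.** Unclear caries and furcation sites may still receive a score on the 5-point scales, clarity is part of the primary endpoints in 8.2, and overlapping contacts are compared in 8.4. Prostheses that obscure the CEJ or caries borders are an exclusion, which removes one cause of unreadable sites.
- **The direction is not general.** It depends on which view fails more, on the endpoint, and on whether pairwise means complete pairs or each view's available sites.
- **The size is assumed.** If the rate really is minimal, say 2% v 0%, the shift is 1.6 points.

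All four stand as limits on the claim. They do not close the gap. Clarity and overlap results do not feed into sensitivity, specificity or AUC. No alternative is stated for a mm reading without a visible landmark. The reason given for a minimal rate does not address visibility.

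**Conclusion.** The point holds in conditional form. The plan has one stated handling, pairwise deletion, and no rule for sites that a view cannot show or measure. On its own rationale those failures depend on the view and probably on disease depth, although Section 1 says this of vertical bone loss, furcation and root caries and not of contact overlap.

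If such sites are deleted as missing, the visibility part of any difference leaves the accuracy comparison. For caries and furcation sensitivity the size is about 0.80 times the difference in unreadable rates, given equal sensitivity of 0.80 on readable sites: 1.6 to 12.0 points over the assumed range. The shift is towards no difference if horizontal failures predominate and runs the other way if vertical fails more. For mm readings the paired comparison would apply only to sites that both views can measure, probably without the deepest ones; the mm difference itself may be unbiased. The change should be made, because it is cheap and bears on the primary objective.

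**What to change.** In 8.5, record not assessable as a result for each surface and view, separate from an evaluation that was never made. Then:

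- **Sensitivity (main analysis).** Keep every reference-standard-positive site and count not assessable as not detected.
- **Specificity.** Show it twice: with unassessable healthy sites counted as not correctly classified, and with them excluded. Scoring them as negative would credit the view that failed.
- **McNemar.** Define it as correct v not correct against the reference standard, in place of presence v absence.
- **ROC/DeLong.** State how these sites enter. One option is the AUC on sites assessable in both views, labelled as such, beside the all-sites sensitivity and specificity.
- **Assessability.** Report the paired difference in % not assessable with a 95% CI that allows for clustering within patient.
- **Bone level.** Give the number of sites each view could measure beside the Wilcoxon comparison.
- **Pairwise deletion.** Keep it as the sensitivity analysis, and state that it means complete pairs.

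The cost is one scoring code and some SAP text. The downside is that reported sensitivity and specificity become less favourable in proportion to the unreadable rate; at 20% unreadable, a sensitivity of 80% on readable sites becomes 64%.

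### Section 8.6 gives an undefined, unit-free r for the Wilcoxon and McNemar tests, and no interval is planned for the paired differences in bone level, detection, sensitivity or specificity

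*Combined protocol and SAP*

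**What the plan says.** Section 8.2 lists three primary endpoints: "Detection of approximal caries (presence and clarity"), "Alveolar bone level measurements (in mm") and "Presence and clarity of furcation involvement". Section 8.4 assigns two paired tests to them. The Wilcoxon signed-rank test is "Used to compare the mean alveolar bone loss measurements (mesial, distal, and total) between vertical and horizontal bitewings". The McNemar test is "Applied to assess paired binary outcomes (e.g., presence vs. absence of caries or furcation involvement) between imaging modalities".

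For the results of these two tests, section 8.6 says: "For Wilcoxon and McNemar tests, effect sizes (r) were reported". The next line reads: "For ROC analysis, 95% CI of AUCs and comparison P-values were provided". Section 8.2 also plans sensitivity and specificity with 95% intervals, for each radiographic method and for caries and furcation only. The descriptive part of section 8.4 plans mean and SD for continuous variables such as bone level, and counts with percentages for categorical variables.

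**The concern.** The plan uses confidence intervals for AUC, sensitivity and specificity but not for the contrasts that its two paired tests examine. Bone level is affected most. It is a primary endpoint in mm, and the sensitivity and specificity intervals do not cover it. Its planned output is a test, a mean and SD, and r.

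Section 7 sizes the trial on a mean difference, yet no section plans to report such a difference with its uncertainty. With 20 patients, a P-value and an r do not tell a reader which differences the data exclude. A non-significant result could then be taken as equivalence of the two views, or a significant one as a difference of useful size, without the evidence to judge either.

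**Working it through.** **Which contrasts have an interval**

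- AUC: 95% CI and a comparison P-value (8.6), with DeLong's test (8.2).
- Sensitivity and specificity: 95% CI for each method separately (8.2).
- Bone level: Wilcoxon test, mean and SD (8.4), r (8.6). No interval.
- Paired detection: McNemar test (8.4), r (8.6). No interval.

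The missing intervals cannot be computed from the listed summaries. Two means give a point difference in mm, but its standard error needs the SD of the within-patient differences, which is not planned. Two separate sensitivity intervals do not give an interval for their paired difference without the discordant counts, which the plan does not undertake to report.

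**r for McNemar**

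The plan has no figure for r to reproduce, so the counts here are assumed: 80 pairs (section 8.1 has 80 vertical and 80 horizontal images), with b = 15 and c = 5 discordant. The usual form, also assumed, is r = Z/√N.

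- Z = (b − c)/√(b + c) = 10/√20 = 2.236
- N = 20 discordant pairs: r = 2.236/4.472 = 0.50
- N = 80 pairs: r = 2.236/8.944 = 0.25
- N = 160 observations: r = 2.236/12.649 = 0.18

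On the same data:

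- Paired difference = (15 − 5)/80 = 12.5 percentage points
- SE = √(20 − 10²/80)/80 = √18.75/80 = 0.0541
- 95% CI = 0.125 ± 1.96 × 0.0541, that is 1.9 to 23.1 points

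This interval treats the 80 pairs as independent. With four pairs per patient they are not, so it is naive.

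**r for Wilcoxon**

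One simulated set of 20 paired differences was multiplied by 0.1, 1 and 5. Z stayed at 2.73, so r stayed at 2.73/√20 = 0.61 (or 2.73/√40 = 0.43 if N counts observations). The Hodges-Lehmann differences were 0.05, 0.45 and 2.26 units. One value of r is thus compatible with a fifty-fold range in the size of the difference, and N is as open here as for McNemar.

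**Expected precision for bone level**

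Section 7 gives a difference of 2.1, an SD of 5.2 and 20 patients. It does not state the endpoint or unit, or whether 5.2 is the SD of paired differences or of each modality. The half-width is t(0.975, 19) × SD of differences/√20, with t = 2.093.

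- If 5.2 is the SD of differences: 2.093 × 5.2/4.472 = 2.43
- If 5.2 is a per-modality SD, the SD of differences is 5.2 × √(2(1 − ρ)):
  - ρ = 0: SD 7.35, half-width 3.44
  - ρ = 0.5: SD 5.20, half-width 2.43
  - ρ = 0.82: SD 3.12, half-width 1.46

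The last case is included because a two-sided paired t-test on section 7's inputs reaches 80% power at n = 20 when ρ is about 0.82. If 5.2 is the SD of differences, the same test needs 51 patients. That mismatch is a separate question. These are t-intervals for a mean and serve only as a guide to the precision of a Hodges-Lehmann interval.

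**The case against.** The best defence is that r is not the only output. A reader might infer from section 8.6 that it is, but section 8.4 supplies means, SDs and percentages, and section 8.2 supplies intervals for each method. A point difference in mm can be formed, and the binary endpoints are not without any interval. This stands. What is missing is the interval for the paired contrast.

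Second, the primary objective is accuracy. For caries the plan addresses it with AUC against a reference standard, AUC intervals and DeLong's test. A raw difference in detection is not accuracy, because extra detections may be false positives. This also stands, and it shapes the fix: paired differences in sensitivity and specificity come first. It does not help bone level, which has no such interval.

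Third, a reader might infer that r for McNemar has no unique value. It is undefined in this plan, but a stated formula and N would make it unique. Nor may the dependence on N be shown by keeping 15 v 5 and raising the number of pairs, say from 80 to 320 (assumed). That changes the result itself, from 12.5 to 10/320 = 3.1 points, so r on pairs should fall. Only 0.50, 0.25 and 0.18 on the same 80 pairs make a fair contrast.

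Fourth, a reader might infer that the interval must be wider than the 2.1 for which the trial is sized. The documents do not settle this. It holds at a half-width of 2.43 but reverses at 1.46. On the per-modality reading the turning point is where √(2(1 − ρ)) = 2.1/2.43, or ρ of about 0.63.

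**Conclusion.** The point holds as a gap in reporting. Section 8.6 leaves r undefined for both paired tests, and no section plans an interval for the paired difference in bone level, detection, sensitivity or specificity. The gap is clearest for bone level.

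On one assumed data set r ranges from 0.18 to 0.50 with the choice of N, against a paired difference of 12.5 points (naive 95% CI 1.9 to 23.1). The discordant counts and the simulated differences are illustrations, not figures from the plan. The bone-level half-width of 1.46 to 3.44 depends on how 5.2 is read and on a within-patient correlation that the plan does not give. The point does not bear on whether the tests themselves are valid. It is a cheap improvement.

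**What to change.** Amend section 8.6 as follows.

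- **Bone level:** report the Hodges-Lehmann paired difference in mm (mesial, distal and total) with a 95% CI. It matches the Wilcoxon test.
- **Caries and furcation:** report the paired differences in sensitivity and in specificity between the two views, each with a 95% CI. Add the raw difference in detection proportion with its CI, and the discordant counts, as a supplement.
- **Unit:** compute all these intervals with the patient as the resampling or clustering unit, because each patient contributes several images and sites.
- **r:** if it is kept, state its formula and its N for each test.

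The cost is SAP wording and a modest extra analysis, mainly a patient-level bootstrap, which may need a short script beyond standard test output. It needs no new patients, images or readings, since the paired data are part of the design.
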